Needs BC and CRC screening You already understand the benefit of having Pap tests but might not know that BC and CRC start as a single cell which can grow and divide for a long time before you would be aware you had these cancers. If BC or CRC isn't found early, it can spread to other parts of your body making it hard to treat and may cost you your life. The good news is that these cancers can be found early – before they spread and when almost all women are completely cured. Needs BC, CRC, and CC Many women don't realize that BC, CRC and CC all start as a single cell which can grow and divide for a long time before you would be aware you had cancer. If this cancer isn't found early, it can spread to other parts of your body may cost you your life. The good news is that these cancers can be found early – before they spread and when almost all women are completely cured.

4.2 Tailored DVD

The TIDVD will include a CC screening component and barriers unique to rural women that are identified during focus groups. The TIDVD will be mailed to a participant and played on a regular DVD player. Bluray player, or computer. The participant interacts in real time with the DVD by answering questions posed by the DVD program and using arrow keys on the remote to highlight and enter their response. All possible tailored messages and videos are included in the TIDVD program with algorithms that provide individualized messages and videos tailored to individual data. The TIDVD format was selected for three reasons. First, the majority of women in rural areas have a DVD player. Secondly, the DVD can be programmed such that women can answer questions using the remote control allowing delivery of tailored messages in real time. We can program a DVD to deliver health messages with visual aids such as graphs, video clips, and storytelling. Once data are obtained from the individual, the program delivers a message developed specifically to the data provided in real time. For example, a message about the barrier of embarrassment with CRC screening would be delivered only if the participant indicated she was embarrassed about the test. We are tailoring on multiple barriers, as well as age and rural residence.³²⁻³⁴ Third, DVD can be duplicated guickly with minimal expense and mailed to participants. The tailored program begins with a generic introduction that explains the use of arrow keys on the remote control to enter responses and asks a few basic questions to determine adherence to each of the 3 screening tests, as well as age (in decade), race, and family history. Responses to questions are stored in memory and integrated into responses (obtained throughout the program) to queries about belief constructs (perceived risk, benefits, and self-efficacy). Throughout the TIDVD program, women will receive programmed tailored messaging bundled to their screening status on BC, CC, and CRC (Table 6). Risk messages are tailored to both perceived and objective risks. For barriers, a list of potential barriers will be presented and women will indicate up to three barriers for the relevant test. The DVD program ends with the narrator encouraging viewers to make an appointment for any of the screenings needed. Screens will be narrated along with the critical information appearing as written text, allowing women with low literacy to use the program. On average, our previous interactive CRC DVD program required 10 minutes to complete, so we anticipate this TIDVD program covering BC, CC, and CRC screening information to take no longer than 30 minutes to complete if the participant chooses to watch all components of all three screening sections. Program coding will be done using DVD Studio Pro.

4.3 Tailored DVD + PN

The second intervention group will receive a TIDVD intervention followed by a telephone call from a PN. **4.3.1 PN Intervention**

PNs will attempt to contact participants by telephone within 1 week after mailing the DVD. PNs will make at least 10 attempts at different times and on different days, including weekends, if needed. This timeframe will allow women to have received the DVD and watched it. If not viewed, the PN will encourage women to view the DVD and will assist to facilitate this. The PN will reinforce the DVD message and address barriers to receiving needed screening tests, including those not mentioned in the DVD. PNs will complete electronic encounter forms during each participant contact and have a file for each navigated participant. The encounter forms will include: 1) days/times of contact attempts; 2) a summary of the telephone call with documented cancer screening barriers; 3) navigator actions to address screening barriers; and 4) time spent on the call. PNs will track any other actions taken to assist participants (e.g. arrange transportation)

and track the time taken to complete those actions. PN information will be directly submitted to a database that will alert them when a follow-up action needs to be placed for a participant (e.g. an alert will be sent to the PN to call the participant to remind them of a cancer screening appointment). PNs will make as many contacts as needed to assist participants to complete screening tests.

4.3.2 PN Qualifications and Training

The success of a PN intervention is dependent upon the navigator's ability to communicate with a wide range of people and in the culturally accepted vernacular. Personal skills such as the ability to be empathetic, patient, and caring are important when it comes to helping participants understand and comply with cancer screening tests. PNs will be trained by [name] and [name], and will include information about cancer screening, treatment, and ways to overcome barriers to health care. Navigators will be trained jointly by OSU and IU staff, and training will include an explanation of the PN role as serving as a link between the participants and the health care system to guide participants to complete needed cancer screening tests. The following criteria will be assessed prior to allowing the PN to begin: 1) ability to communicate; 2) knowledge/understanding of cancer screening; and 3) understanding of the community and cultural setting.

4.4 Intervention Pretesting

Usability testing will occur using both individual user feedback and CAB member discussions. The CAB will be actively involved in development and evaluation of the PN and TIDVD interventions to ensure clarity, relevance and sensitivity. Usability will be evaluated by assessing ease of use, content (leveling and appropriateness), aesthetic appeal, and cultural relevance. We will present prototypes to members of the target population either individually or in group sessions as components are designed. The information gathered during testing sessions will be used to revise both interventions as needed.

4.5 Usual Care (UC)

Women randomized to UC will receive brochures developed by the research team using national guidelines and/or existing, current brochures developed by those organizations that explain and provide encouragement for BC, CC, and CRC screening. Women will receive these after the active intervention phase is complete.

4.6 Potential Risks

No risks are anticipated from baseline or follow-up surveys. Risks anticipated with receiving the intervention materials (brochures, DVD, PN call(s)) or encouraging participants to obtain BC, CC, and/or CRC screening exams are minimal, e.g., embarrassment or unnecessary fear of cancer.

4.7 Protection against Potential Risks

We anticipate no risks. Only persons directly involved with the study will have access to data identifying individuals. Records and forms will be kept in locked file cabinets when not in use. No names will be stored on computer files for data analysis, and no individuals will be identified in the results of this study. Access to computer-stored information will require simultaneous knowledge of the data format, computer language, file name and password. Participants will be told that they do not have to answer any questions they do not want to answer.

4.8 Potential Benefits

The participants may not benefit directly from the study, however, benefits to the subjects may come in the form of increased awareness and use of cancer screening tests for the detection of BC, CC, and/or CRC. The subjects and society in general will benefit through the knowledge gained in promoting knowledge about cancer control with the future benefits of lower mortality from cancer. The benefits far outweigh the risks of this study, since even the possible risks, mainly unnecessary fear of cancer, might prompt participation in screening, which is in itself of benefit to the subject.

5.0 Data Handling and Analyses

5.1 Statistical Analysis

5.1.1 Sample Size

Estimates of effect size (Table 5) for the intervention at 12 months is based on our experience in projects promoting screening among underserved populations. We estimate 10% attrition at 12 months, when our primary outcome will be assessed. Attrition of 10% is conservative because we will have medical record data on most of the persons who drop out which will reduce the effect of drop out on the primary outcomes. We based power calculations on 2-sided tests when comparing the two intervention arms (TIDVD vs. TIDVD+PN) because we could not be certain which group would perform better. Because of the overwhelming evidence in the literature^{35,36} that the UC arm does not have better screening rates than tailored DVD or PN interventions, we based the power calculations on 1-sided tests for comparisons to the control group (TIDVD vs. UC; TIDVD+PN vs. UC). The planned statistical analyses are consistent with these power calculations. Specifically, we will use two sided tests for TIDVD vs. TIDVD+PN, and the 1-sided tests for comparing interventions to the UC arm, using the 1-sided p-value from the Z statistic in contingency table analysis and from the likelihood ratio test in logistic regression analysis. To achieve 80% power for the contingency table analyses, and the likelihood ratio tests of logistic regression for the primary outcome of adherence to all needed screening tests at 12 months by MRR, a sample size of 356 per each intervention group and 180 in the UC group will be needed, which will require 396 per intervention group and 200 in the UC group at baseline to account for attrition. For 80% power for the secondary outcome of adherence to any needed (BC or CC or CRC) test, regardless of the number of screening tests needed, a sample size of 376 per each intervention group and 200 in the UC group will be required at 12 months. We will require 418 per intervention group and 222 in the UC group at baseline to account for attrition and to achieve at least 80% power for both outcomes. The total sample size is 1058 participants enrolled with 418 randomized to each intervention arm and 222 randomized to the UC arm.

Table 5.	Samp	le Size'
----------	------	----------

Effect sizes for screening at 12 months	Control (UC) 12 Months	TIDVD 12 months	TIDVD+ PN 12 months	TIDVD+PN at baseline for	control arm (UC) at baseline for 80% power at 12 months	TIDVD+PN	-	Power TIDVD vs. TIDVD+ PN	TIDVD vs. control	Power TIDVD+ PN vs. Control (UC)
Cervical	35%	50%	70%	NA	NA	NA	NA	NA	NA	NA
Breast	35%	45%	65%	NA	NA	NA	NA	NA	NA	NA
Colon	30%	40%	55%	NA	NA	NA	NA	NA	NA	NA
All needed screenings (primary outcome)	10%	20%	30%	396	200	356	180	82%	83%	99%
Any (at least 1) needed screening (secondary outcome)	25%	35%	45%	418	222	376	200	80%	80%	99%

*Estimates of effect sizes for the secondary outcome (at least 1 needed test adhered to by 12 months) was based on the most conservative single test (i.e., colon cancer screening). Effect sizes for the primary outcome were based on an estimated reduction of 5% in the number of participants who would adhere to all needed tests compared to only one of the needed tests. Power columns are based on the most stringent required sample size, i.e., when N=418 per each intervention arm and N=222 controls at baseline and projected 376 per each intervention arm and 200 controls at 12 months.

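### Table 5's planning rates do not match the sources its footnote gives for them, in both the any-needed row that sets N = 1058 and the primary-outcome row

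*Combined protocol and SAP*

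**What the plan says.** Section 5.1.1 and Table 5 size the trial on two composite outcomes.

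- **Secondary outcome.** The row "Any (at least 1) needed screening (secondary outcome)" lists 25%, 35% and 45% for UC, TIDVD and TIDVD+PN, with power of 80% (TIDVD vs TIDVD+PN), 80% (TIDVD vs UC) and 99% (TIDVD+PN vs UC). The text says that for this outcome "a sample size of 376 per each intervention group and 200 in the UC group will be required at 12 months". Allowing for 10% attrition gives 418 and 222 at baseline, hence 418 + 418 + 222 = 1058.
- **Source of those rates.** The footnote says the estimate "was based on the most conservative single test (i.e., colon cancer screening"). The Colon row of the same table reads 30%, 40% and 55%.
- **Primary outcome.** The all-needed row lists 10%, 20% and 30%, with power of 82%, 83% and 99% in the same order. The footnote derives these rates from a 5% reduction relative to completing only one needed test. It adds that the power columns assume 376 per intervention arm and 200 controls at 12 months.
- **Tests.** The section says "we based the power calculations on 1-sided tests for comparisons to the control group (TIDVD vs. UC; TIDVD+PN vs. UC)" and "We based power calculations on 2-sided tests when comparing the two intervention arms (TIDVD vs. TIDVD+PN)". It gives no alpha.

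**The concern.** The any-needed row is the more demanding of the two and sets the size of the trial, so its rates should be traceable. The footnote points to the Colon row, but the figures are lower by 5, 5 and 10 points. No uniform shift links the rows, and the gap between TIDVD and TIDVD+PN shrinks from 15 points to 10.

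The choice of rates moves the two contrasts in opposite directions. With the 10-point gap between TIDVD and UC unchanged, lower rates raise power. For TIDVD vs TIDVD+PN, the narrower gap lowers it. Calling the basis conservative therefore does not tell the reader which contrast is protected.

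The same footnote is also out of step with the primary row. A 5-point reduction from 25/35/45 gives 20/30/40, not 10/20/30. A relative reduction does not help, since 0.95 × 25% = 23.75%. At stake is whether a reader can tell which rates the primary outcome was powered for.

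**Working it through.** **Inputs.** The rates, numbers and stated powers are from Table 5. Sidedness is from section 5.1.1. Alpha = 0.05 per comparison is an assumption, adopted because it reproduces the any-needed row.

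**Formula** (two-proportion Z test, pooled variance under the null):

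- p̄ = (n₁p₁ + n₂p₂)/(n₁ + n₂)
- s₀ = √[p̄(1 − p̄)(1/n₁ + 1/n₂)]
- s₁ = √[p₁(1 − p₁)/n₁ + p₂(1 − p₂)/n₂]
- power = Φ[(|p₂ − p₁| − z·s₀)/s₁], with z = 1.645 (one-sided) or 1.960 (two-sided)

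**Step 1: reproduce the any-needed row at 25/35/45.**

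- TIDVD vs UC, 376 and 200, one-sided: s₀ = 0.04066, s₁ = 0.03928; (0.10 − 1.645 × 0.04066)/0.03928 = 0.843, power 80.0% (stated 80%).
- TIDVD vs TIDVD+PN, 376 each, two-sided: s₀ = 0.03573, s₁ = 0.03554; (0.10 − 1.960 × 0.03573)/0.03554 = 0.843, power 80.0% (stated 80%).
- TIDVD+PN vs UC: 99.9% (stated 99%).
- Solving for 80% power gives 375.6, so 376 per intervention arm (35 vs 45), and then 200 UC (25 vs 35). Dividing by 0.9 gives 417.8 and 222.2, matching 418 and 222.

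The row is internally correct.

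**Step 2: the colon rates, same numbers.**

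- 30 vs 40: s₀ = 0.04214, s₁ = 0.04109; (0.10 − 1.645 × 0.04214)/0.04109 = 0.747, power 77.2%.
- 40 vs 55: s₀ = 0.03642, s₁ = 0.03601; (0.15 − 1.960 × 0.03642)/0.03601 = 2.183, power 98.5%.

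For 30 vs 40, other test forms give 78.5% (unpooled), 77.5% (arcsine), 76.4% (log odds ratio) and 74.3% (continuity-corrected), all below 80%.

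**Step 3: the primary row at 376/200.**

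| Rates | TIDVD vs UC | TIDVD vs TIDVD+PN |
|---|---|---|
| Stated in Table 5 | 83% | 82% |
| 10/20/30 as printed | 94.2% | 88.8% |
| 20/30/40 (any-needed minus 5 points) | 83.9% | 82.1% |

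The 20/30/40 figures match the stated ones if the table drops decimals, as it appears to do when 99.9% is printed as 99%. The stated requirement of 356 per intervention arm points the same way: 80% power, two-sided, needs 355.9 per arm for 30 vs 40, but only 293.2 for 20 vs 30.

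**The case against.** The case for leaving the table alone has several parts.

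- **No miscalculation in the any-needed row.** This stands: 80% is right for 25 vs 35 and for 35 vs 45. A reader might infer that the stated 80% is wrong and the true figure is 77%. The documents do not support that. The footnote says the estimate was based on colon screening, not that it equals the colon rates, and a discount from them is a plausible reading. But the discount is not uniform and is nowhere described.
- **Any-needed below every single test.** A reader might infer that 25/35/45 is impossible, since completing at least one needed test cannot be rarer than completing a particular needed test. That requires a common denominator, which Table 5 does not give. The single-test rows are not labelled as needed tests. Their UC values (35%, 35%, 30%) lie close to the 36%, 32% and 30% that section 2.1 reports for Pap test, mammography and CRC test in an observational sample of rural women. The trial enrolls only women overdue for at least one test.
- **Conservatism.** For TIDVD vs TIDVD+PN the row is strongly conservative: 80%, against 98.5% at colon rates. Hypothesis 1 compares TIDVD+PN with TIDVD and with UC; TIDVD vs UC, the only contrast that loses power, is not among its stated comparisons, although Aim 1 covers all three arms.
- **Attrition.** The plan calls 10% conservative because medical records will cover most dropouts. With no loss (418 and 222), power for 30 vs 40 is 81.0%.

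These points limit the consequence. They do not explain the step from the Colon row, and none bears on the mismatch in the primary row.

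**Conclusion.** Table 5's rates and footnote disagree in two places.

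For the any-needed outcome, the stated 80% holds at the printed rates. At the colon rates, TIDVD vs UC falls by just under 3 points to about 77%, while TIDVD vs TIDVD+PN rises to about 98.5%. This affects one contrast of a secondary outcome and does not show that the trial is too small.

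For the primary outcome, the printed 10/20/30 is 15 points below any-needed instead of 5, and its stated power does not follow from it: about 94% and 89%, against 83% and 82%. The stated power and the 356 per arm both fit 20/30/40. That suggests which rates were used in the calculation, but the documents do not settle which rates were intended. On either set the primary outcome has more than 80% power for both contrasts at 376/200.

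The figures rest on alpha = 0.05 per comparison, which is inferred; sidedness is as stated in section 5.1.1.

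**What to change.** Reconcile Table 5 and its footnote, and state the alpha.

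1. **Any-needed row.** Either keep 25/35/45, state how it was derived from the colon rates, and add that TIDVD vs UC power is about 77% at 30 vs 40; or enter 30/40/55 and restate power as about 77% (TIDVD vs UC) and 98-99% (TIDVD vs TIDVD+PN).
2. **Primary row.** Either correct the printed rates (20/30/40 reproduces the stated power); or keep 10/20/30, restate power as about 94% and 89%, correct the footnote's 5%, and revisit the 356 per arm given for this outcome. If 30/40/55 is entered in step 1, then 20/30/40 lies 10, 10 and 15 points below it, so the 5% must be reworded in that case too.

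The cost is edits to the table, the footnote and a sentence or two of section 5.1.1. Enrollment and the planned analyses stay as they are.

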2.0 BACKGROUND AND RATIONALE

2.1 Magnitude of the Problem

The cancer burden among rural and underserved populations is significant. Residents living in rural areas in the U.S. experience higher cancer incidence and mortality rates, as well as lower screening rates.¹⁻⁵ The breast cancer mortality rates in the 32 targeted Ohio and Indiana counties are 9.7% and 5.8% greater, respectively, than that for the U.S., while the cervical cancer mortality rate is 12.5% greater, and the CRC mortality rates are 10.4% and 6.1% greater, respectively, than that for the U.S. This results in 106 excess deaths in these counties per year. Reasons for cancer disparities among rural populations are due to many social determinants of health including lower socioeconomic status (SES), lower educational levels, lifestyle factors, genetics, limited access to healthcare, lack of health insurance, or a combination of these factors.³⁻⁶ Screening adherence rates for BC, CC, and CRC cancers, for which there are validated screening tests available, are lower for those with less education, a proxy for SES.^{7,8} The rural counties targeted for this project (Figure 1), include mainly White, poorer, and less educated populations with limited access to health care. Thus, it is essential to intervene in these rural counties to reduce cancer disparities. Many rural women do not complete screening at recommended intervals.⁵ In a recently completed observational study among rural women in Ohio, medical record validated completion of screening within recommended guidelines was: 32% for mammography, 36% for Pap test, and 30% for a CRC test.⁹ Only 8.6% had completed all three tests within guidelines.⁹This suggests the need for cost effective interventions to provide rural women with the latest information about screening recommendations and needed tests.^{10,11}

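### Table 5's primary-outcome rates (10/20/30%) yield neither its sample size nor its power at alpha 0.05, and they contradict its own 5% footnote; enrolment of 1058 is unaffected

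*Combined protocol and SAP*

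**What the plan says.** Section 5.1.1 sizes the trial on two outcomes. For the primary outcome (all needed screenings by 12 months), "a sample size of 356 per each intervention group and 180 in the UC group will be needed" for 80% power, "which will require 396 per intervention group and 200 in the UC group at baseline to account for attrition". The secondary outcome (any needed screening) needs 376/200 at 12 months. That is inflated to 418/222 "to achieve at least 80% power for both outcomes", which gives 2 × 418 + 222 = 1058.

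Table 5 prints:

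| Outcome | UC / TIDVD / TIDVD+PN | 12-month N, each intervention arm / UC | Power: TIDVD vs TIDVD+PN, TIDVD vs UC, TIDVD+PN vs UC |
|---|---|---|---|
| All needed (primary) | 10 / 20 / 30% | 356 / 180 | 82%, 83%, 99% |
| Any needed (secondary) | 25 / 35 / 45% | 376 / 200 | 80%, 80%, 99% |

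The footnote makes three statements:
- On the primary rates: "Effect sizes for the primary outcome were based on an estimated reduction of 5% in the number of participants" when all needed tests, and not just one, must be completed.
- On the power columns: "Power columns are based on the most stringent required sample size", which is 376/200 at 12 months.
- On the secondary rates: the effect size "was based on the most conservative single test (i.e., colon cancer screening").

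On sidedness, "We based power calculations on 2-sided tests when comparing the two intervention arms"; comparisons with UC are one-sided. No alpha is given.

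**The concern.** Two things in the primary row do not fit.

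- **Footnote against rates.** A 5% reduction from 25/35/45% cannot give 10/20/30%. The gap is 15 points in each arm.
- **Rates against N and power.** Both rows assume 10-point steps, but the primary rates lie further from 50%, so their variance is smaller. At a common alpha, the primary row should show a clearly smaller N and clearly higher power than the secondary row. The printed differences are small (356 against 376; 82%/83% against 80%/80%).

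This row is the only numerical justification for the primary outcome. A UC rate of 10% against 20% is a two-fold difference in the assumed control rate. The same 10-point gain for TIDVD over UC is a relative risk of 2.0 in the first case and 1.5 in the second. A reader cannot tell which effect the trial was designed to detect.

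**Working it through.** **Inputs.** Rates, N and power come from Table 5. Target power (80%), sidedness and 10% attrition come from 5.1.1. Alpha = 0.05 is an assumption, tested in step 1.

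**Formulas** (pooled-variance two-proportion Z test, with difference Δ):
- N per arm, equal arms = [z(1−α/2)·√(2p̄(1−p̄)) + z(0.80)·√(p1(1−p1) + p2(1−p2))]² / Δ²
- Power = Φ[(Δ − z·s0)/s1], where s0 = √(p̄(1−p̄)(1/n1 + 1/n2)), s1 = √(p1(1−p1)/n1 + p2(1−p2)/n2), and z is 1.960 (two-sided) or 1.645 (one-sided)

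**Step 1: secondary row, 25/35/45%.**
- TIDVD vs TIDVD+PN: (1.3579 + 0.5800)²/0.01 = 375.6, so 376 (printed 376).
- Its power at 376/376: (0.10 − 1.960 × 0.03573)/0.03554 = 0.843, giving 80.0% (printed 80%).
- TIDVD vs UC at 376/200: p̄ = 0.3153; (0.10 − 1.645 × 0.04066)/0.03928 = 0.843, giving 80.0% (printed 80%). The smallest UC arm reaching 80% is 200 (printed 200).

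Method and alpha therefore reproduce the plan's own secondary figures.

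**Step 2: primary row as printed, 10/20/30%.**
- N: (1.2002 + 0.5119)²/0.01 = 293.2, so 294 per intervention arm (printed 356).
- UC N: 106 with the intervention arm held at 356, 112 with it at 294, 121 at ratio 356:180, 123 at ratio 376:200 (printed 180).
- TIDVD vs TIDVD+PN at 376/376: (0.10 − 1.960 × 0.03158)/0.03137 = 1.215, giving 88.8% (printed 82%).
- TIDVD vs UC at 376/200: p̄ = 0.1653; (0.10 − 1.645 × 0.03251)/0.02959 = 1.573, giving 94.2% (printed 83%).
- TIDVD+PN vs UC: above 99.9%, consistent with the printed 99%.
- At the row's own 356/180, power is about 87% and 92.3%, so using the smaller N does not explain the entries.

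Other test forms do not recover them either: 87.1%/92.6% with continuity correction and 88.8%/93.8% with the likelihood ratio. Simulation of the Z test (400,000 runs) gives 88.9%/94.4%.

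**Step 3: the footnote's rule, 25/35/45% minus 5 points = 20/30/40%.**
- N: (1.3221 + 0.5646)²/0.01 = 355.9, so 356 (printed 356). UC N is 175 to 179, depending on the allocation convention (printed 180).
- TIDVD vs TIDVD+PN at 376/376: (0.10 − 1.960 × 0.03479)/0.03459 = 0.920, giving 82.1%.
- TIDVD vs UC at 376/200: p̄ = 0.2653; (0.10 − 1.645 × 0.03864)/0.03686 = 0.989, giving 83.9%.
- At 356/180: 80.0% and 80.8%, in line with the 80% stated in 5.1.1.
- Baseline: 356/0.9 = 396 and 180/0.9 = 200, as printed.

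**Step 4: 5% read as a relative reduction, 23.75/33.25/42.75%.** This needs 409 per intervention arm and gives 76.6%/77.4% at 376/200, so it does not explain the row.

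**The case against.** The strongest reply is that alpha is never printed and could have been tightened for the primary outcome alone. With 0.025 two-sided and 0.0125 one-sided, 10/20/30% gives 356 per intervention arm and 82.4%/82.0% at 376/200, close to the print. If so, the rates stand and only the footnote is wrong. Against this:

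- No section mentions an alpha split.
- UC would need 192, not 180. At 356/180, TIDVD vs UC has 77.9% power, below the 80% claimed.
- At that alpha the secondary row would need 455 per arm and have 71%/59% power at 376/200, so the split would have to apply to one row only.
- The 15-point gap against the stated 5% remains at any alpha.

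What stands is that the N and power findings are conditional on alpha 0.05. The footnote conflict is not.

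The 99% entries correspond to values above 99.9%, so the table may truncate. Truncated, 20/30/40% prints as 82/83/99, exactly as shown, and 83% need not be an error under those rates.

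Section 2.1 ("Only 8.6% had completed all three tests within guidelines") might seem to support a 10% UC rate. It is weak evidence: it describes an observational sample and all three tests. The trial enrols women overdue for at least one test and counts only the tests each woman needs. It does not settle which entry is the misprint.

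**Conclusion.** The concern holds. The primary row's rates contradict its footnote (15 points against 5%) at any alpha. At the alpha that reproduces the secondary row, those rates also fail to give the row's N (294 and about 106 to 123, against 356 and 180) and two of its three powers (88.8% and 94.2%, against 82% and 83%). Rates of 20/30/40% fit the footnote and nearly all of the row, but the documents do not establish that these were the rates used.

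The consequence is limited. If 10/20/30% is right at alpha 0.05, power is understated. Under either 10/20/30% or 20/30/40% at that alpha, every primary comparison exceeds 80% at 376/200. Only the relative reading of 5% falls below, at about 77%, and it does not match the printed N. The secondary outcome sets enrolment at 1058, which does not change. This is a reporting error that should be fixed.

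**What to change.** The authors should say which rates were assumed, then make the row agree with them:

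- **If 20/30/40%:** print those rates and keep 356/180 and 396/200. Give power at 376/200 as 82%/84%/>99%, or keep 83% and 99% with a note that values are truncated.
- **If 10/20/30%:** restate the 12-month N as about 294 per intervention arm, with the UC N and its allocation convention. With 10% attrition the baseline is 294/0.9 ≈ 327 per arm and about 118 to 137 UC (106/0.9 to 123/0.9), replacing 396/200. Give power at 376/200 as 89%/94%/>99%, change the footnote's 5% to the 15 points used, and correct 356/180 and 396/200 in the text of 5.1.1.

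In either case, print the alpha for each row. If a smaller alpha was used for the primary outcome, state it and recompute that row accordingly. The footnote should also explain how 25/35/45% was derived from the colon row, which reads 30/40/55%. The secondary row's N and power need no change.

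The cost is one table row, its footnote and one sentence. There are no extra participants and no change to the analysis.
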